### **4.2. Secondary outcomes**

- Between-group changes in visceral adipose tissue mass between baseline and month 12

[Time Frame: 12 months] [Unit: L] [Variable: Continuous]

Assessed by magnetic resonance imaging (MRI)

- Between-group changes in lean tissue mass between baseline and month 12

[Time Frame: 12 months] [Unit: L] [Variable: Continuous]

Assessed by magnetic resonance imaging (MRI)

- Between-group changes in total body fat mass between baseline and month 12  
 [Time Frame: 12 months] [Unit: L] [Variable: Continuous]  
 Assessed by magnetic resonance imaging (MRI)
- Between-group changes in body weight between baseline and month 12  
 [Time Frame: 12 months] [Unit: kg] [Variable: Continuous]  
 Assessed by using a Tanita bioelectrical impedance analysis (BIA) scale
- Between-group changes in glycated hemoglobin (HbA1c) between baseline and month 12  
 [Time Frame: 12 months] [Unit: mmol/mol] [Variable: Continuous]  
 Assessed by routine clinical chemistry
- Between-group changes in Homeostatic Model Assessment for Insulin Resistance (HOMA-IR) between baseline and month 12  
 [Time Frame: 12 months] [Unit: none] [Variable: Continuous]  
 Calculated by multiplying fasting plasma glucose (mmol/L) with fasting serum insulin (mU/L) and dividing the product by 22.5.  
 Assessed by routine clinical chemistry
- Between-group changes in fasting plasma glucose between baseline and month 12  
 [Time Frame: 12 months] [Unit: mmol/L] [Variable: Continuous]  
 Assessed by routine clinical chemistry
- Between-group changes in fasting serum insulin between baseline and month 12  
 [Time Frame: 12 months] [Unit: mU/L] [Variable: Continuous]

Assessed by routine clinical chemistry

- Between-group changes in systolic blood pressure between baseline and month 12

[Time Frame: 12 months] [Unit: mmHg] [Variable: Continuous]

Assessed by using an automated blood pressure monitor

- Between-group changes in diastolic blood pressure between baseline and month 12

[Time Frame: 12 months] [Unit: mmHg] [Variable: Continuous]

Assessed by using an automated blood pressure monitor

- Between-group changes in plasma lipids (total cholesterol, LDL cholesterol, triglycerides, HDL cholesterol, apoB and apoA1) between baseline and month 12

[Time Frame: 12 months] [Unit: mmol/L or g/L (apoB and apoA1)] [Variable: Continuous]

Assessed by routine clinical chemistry

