- Between-group changes in circulating inflammatory markers (CRP, Tumor Necrosis Factor Alpha-receptor 1 and 2, Interleukin-1 receptor antagonist, Fibroblast growth factor 21) between baseline and month 12

[Time Frame: 12 months] [Unit: ng/l or mg/l (CRP)] [Variable: Continuous]

Assessed by routine clinical chemistry and ELISA

- Between-group changes in pancreatic fat between baseline and month 12

[Time Frame: 12 months] [Unit: %] [Variable: Continuous]

Assessed by magnetic resonance imaging (MRI)

- Between-group changes in flow-mediated dilation (FMD) between baseline and month 12

[Time Frame: 12 months] [Unit: %] [Variable: Continuous]

Assessed by ultrasound in approximately half of the study population (n=75)

- Between-group changes in pulse-wave velocity (PWV) between baseline and month 12  
[Time Frame: 12 months] [Unit: m/s] [Variable: Continuous]

Assessed by ultrasound in approximately half of the study population (n=75)

- Between-group values in FMD and PWV at month 12  
[Unit: % and m/s] [Variable: Continuous]

Assessed by ultrasound in the whole population (n=150)

- Between-group changes in liver fat, HbA1c, and blood lipids in prespecified subgroups of type-2 diabetes status (yes/no), gender (male/female), individuals with NAFLD/without NAFLD at baseline, individuals with the CC vs CG/GG I148M genotype in PNPLA3, and in individuals with low respectively high dietary compliance based on dietary and lipogenic biomarkers changes (e.g. linoleic acid, DHA and palmitoleic acid changes from baseline to 12 months) between baseline and month 12

[Time Frame: 12 months]

We will assess whether response to diets in liver fat, HbA1c and blood lipids differ between gender, high vs low compliers, genotype, individuals with prediabetes or diabetes or those who have NAFLD/do not have NAFLD at baseline

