#### **5.2 Subgroups**

Further statistical analyses of the primary and secondary outcomes (liver fat, HbA1c and blood lipids) will be performed in the following prespecified subgroups:

**Type-2 diabetes status:** Subjects will be divided into two subgroups based on type-2 diabetes status (yes/no) of which the other subgroup (“no”) will constitute of subjects without type-2-diabetes but with prediabetes as defined by a fasting plasma glucose between 5.6-6.9 mmol/L and/or an HbA1c value between 39-47 mmol/mol. Type-2 diabetes diagnosis is verified by a clinician using medical records.

**Gender:** Subjects will be divided into two subgroups based on gender (male/female).

**NAFLD status:** Subjects will be divided into two subgroups based on NAFLD status (yes/no) in which NAFLD is defined as a liver fat content exceeding 5.56 % of liver tissue.

**PNPLA3 genotype:** Subjects will be divided into two subgroups based on the I148M variant of the PNPLA3 gene (CC vs CG/GG genotype).

**Compliers:** Subjects will be divided into two subgroups based on dietary adherence (high vs low compliers), assessed using both dietary and lipogenic biomarker changes (e.g. linoleic acid, DHA and palmitoleic acid) between month 0 and month 12.

All subgroup analyses will be conducted as described for the analyses of the full study population.

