## 6. Analyses

Normally distributed variables will be presented as mean  $\pm$  SD and skewed distributed variables will be presented as median (IQR). Continuous variables will be tested for normality using the Shapiro-Wilk W test and skewed data ( $W < 0.95$ ) will be logarithmically transformed or analyzed non-parametrically, where appropriate. Homogeneity of variances between groups will be examined visually. Categorical variables will be presented as counts or percentages (%). An  $\alpha$ -value of 0.05 is set as the significance level.

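### The subgroup plan asks whether response differs between subgroups but only repeats the diet test in ten strata at an unadjusted 0.05, with no interaction test and no exploratory label

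*SAP*

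**What the plan says.** Among the secondary outcomes, SAP section 4.2 lists "Between-group changes in liver fat, HbA1c, and blood lipids in prespecified subgroups of type-2 diabetes status (yes/no), gender (male/female", and goes on to baseline NAFLD, PNPLA3 genotype and dietary compliance. The same item gives the purpose: to see whether the response in these outcomes differs across the levels of each factor. Section 4.3 is a separate list of exploratory outcomes, and the subgroups are not in it.

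Section 5.2 announces "Further statistical analyses of the primary and secondary outcomes (liver fat, HbA1c and blood lipids) will be performed in the following prespecified subgroups", defines five factors with two levels each, and closes with "All subgroup analyses will be conducted as described for the analyses of the full study population".

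The full-population analysis is in sections 6.1 and 6.2. It is a general linear model for the 12-month change, with diet as the factor in 6.1. It adjusts for diabetes status, gender and the baseline value. Pairwise t-tests follow a significant overall result, and effects are reported with confidence intervals and p-values. Section 6 gives one criterion for everything: an alpha "value of 0.05 is set as the significance level".

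The SAP contains no treatment-by-subgroup interaction term, no multiplicity adjustment, no condition that the primary be significant first, and no statement of how a subgroup result is to be interpreted.

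**The concern.** Two things go wrong together.

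First, the analysis does not answer the question asked. Whether response differs between, say, men and women is a question about the difference between two diet effects. Testing the diet effect separately in each level does not test that difference. A result that is significant in one stratum and not in the other is weak evidence of a different response, because the strata differ in size and both estimates are noisy.

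Second, the within-stratum tests re-examine the primary endpoint ten times at the full level, under the heading of a secondary outcome and with no interpretive limit. Prespecification does not control the error over ten overlapping tests. At stake is a report in which the primary is not significant but a diet effect in some stratum is presented as a planned finding.

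**Working it through.** **Inputs from the SAP.** Five two-level factors (5.2), so 5 × 2 = 10 strata. Three diets allocated 1:1:1 (section 2). One level, 0.05 (section 6). A three-arm overall test before pairwise tests (6.1, 6.2). From 2.1: SD 3, difference 2 percentage points, 36 evaluable and 50 randomized per group.

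**The plan's own figure.** Lehr's formula gives 16 × (SD/difference)² = 16 × (3/2)² = 36 per group, as stated, with power 0.807. Allowing for 25% drop-out, 36/0.75 = 48, close to the 50 planned. This sizes the whole-population comparison. An even split would leave about 36/2 = 18 evaluable per arm in a stratum.

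**Upper reference.** If the ten tests were independent, the chance of at least one false positive would be 1 − 0.95¹⁰ = 0.401. They are not independent, because every participant appears in five strata, so the rate was simulated.

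**Simulation for liver fat, no diet effect anywhere.** Three equal arms, five binary factors, and an overall F-test in each stratum at 0.05, with baseline and stratification covariates. There were 4,000 trials per setting. The SAP gives neither the stratum sizes nor the correlation between factors, so both are assumptions.

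| Setting | At least one significant stratum | Same, with non-significant primary |
|---|---|---|
| Independent factors, N = 150, three sets of stratum sizes | 0.301-0.308 | 0.249-0.258 |
| Independent factors, N = 112, three sets of stratum sizes | 0.297-0.303 | 0.250-0.255 |
| Factor correlation 0.5, N = 150 | 0.295 | 0.242 |
| Factor correlation 0.8, N = 150 | 0.253 | 0.205 |

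Without the two compliance strata the first column is 0.26-0.27 with independent factors, and 0.23 at factor correlation 0.8.

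**The directional event.** The figures above count any difference among three arms, in any direction. A narrower event requires three things together: the primary F-test is not significant, some stratum F-test is, and in that stratum the customized diet is significantly better than control. With 5,000 null trials each at N = 111 and N = 150, independent 50:50 factors and no covariates, it occurs in about 7% of trials. For either experimental diet better than control it is about 11%. A favourable two-sided result for one named diet in the full population has a null rate of at most 0.05/2 = 2.5%, and lower once the overall test must also be significant.

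**Interaction tests.** One unadjusted interaction test per factor, five in all, gives at least one false positive in about 22-23% of null trials with independent factors (1 − 0.95⁵ = 0.226), and 18-21% with correlated factors. Changing the test alone therefore does not remove the need for a label.

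**All outcomes.** Section 4.2 names six lipids: "Between-group changes in plasma lipids (total cholesterol, LDL cholesterol, triglycerides, HDL cholesterol, apoB and apoA1) between baseline and month 12". If the subgroup item means these six, there are 1 + 1 + 6 = 8 outcomes, 8 × 10 = 80 overall tests and 80 × 0.05 = 4 expected false positives. The chance of at least one is about 77% to 95% for between-outcome correlations from 0.7 down to 0. This rests on assumed correlations and is secondary to the point.

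**The case against.** The strongest reply is that these are prespecified analyses aimed at effect modification, that secondary outcomes are often tested without adjustment, and that nothing in the SAP lets a subgroup replace the primary. Section 4.1 names one primary outcome, section 5.1 makes the full intention-to-treat population primary, and section 5.2 describes the subgroup work as further analyses.

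Much of this stands. A reader might infer that the plan lets a failed primary be replaced by a stratum result, with a 26-30% chance of a false claim for the customized diet. The documents do not support that. No section gives a subgroup that role. The 26-30% also includes strata where control looks better, or where the two experimental diets differ from each other. The rate for the claim a reader would worry about is about 7%, or about 11% for either experimental diet.

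The appeal to effect modification does not rescue section 5.2, however. It is the stated purpose, and it is what the section fails to test.

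Three further limits apply. The documents give reason to doubt independent factors: section 1 says PNPLA3 variants raise liver fat, so genotype and NAFLD strata are probably related. This lowers the rate only modestly, to about 25% at a factor correlation of 0.8. The count of 80 is not the exact number of planned tests, because sections 6.1 and 6.2 run some outcomes in both analysis populations. Finally, the simulation treats compliance as unrelated to diet and outcome. It is defined by biomarker changes after randomization, so the error in those two strata could be higher.

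**Conclusion.** The point holds. The SAP lists the subgroup effects as a secondary outcome and asks whether response differs, yet it specifies only within-stratum diet tests at an unadjusted 0.05. It has no interaction test, no condition on the primary and no exploratory status.

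Under a complete null, the chance of some significant liver-fat stratum in any direction is about 30% (25-31%). Jointly with a non-significant primary it is about 26% with independent factors, falling to about 20% under strong correlation between factors. The chance of a non-significant primary plus a stratum favouring the customized diet over control is about 7%, and about 11% for either experimental diet.

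These rates rest on assumed stratum sizes and factor correlations, complete data and one overall test per stratum. The liver-fat figures do not depend on how many lipids are meant. The missing interaction test is read directly from the text and needs no assumption.

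**What to change.** Replace the last sentence of section 5.2 with text to this effect:

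> For each subgroup factor, the question of differing response is tested by adding the factor (where not already a covariate) and its interaction with treatment group to the model in section 6.1 or 6.2. Differences between diets within each stratum are reported as estimates with 95% confidence intervals, without declarations of significance and without post-hoc tests. All subgroup analyses are exploratory and cannot support a claim of efficacy, whatever the result of the primary analysis.

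The exploratory statement is needed as well as the interaction test, since five unadjusted interaction tests still give at least one false positive in about 22% of null trials. Moving the item from 4.2 to 4.3 would not be enough, because section 6.2 gives secondary and exploratory outcomes the same model and the same follow-up tests. The item in 4.2 should refer to the revised 5.2 so that its status is clear.

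The change is to SAP wording and its analysis specification, and needs no new data. The cost is that the planned within-stratum p-values and pairwise tests are dropped, and no subgroup result can be presented as established. Whether the protocol would need a matching change cannot be seen from the SAP alone.

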## 6. Analyses

Normally distributed variables will be presented as mean  $\pm$  SD and skewed distributed variables will be presented as median (IQR). Continuous variables will be tested for normality using the Shapiro-Wilk W test and skewed data ( $W < 0.95$ ) will be logarithmically transformed or analyzed non-parametrically, where appropriate. Homogeneity of variances between groups will be examined visually. Categorical variables will be presented as counts or percentages (%). An  $\alpha$ -value of 0.05 is set as the significance level.

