## **2.1. Sample size calculation**

The sample size calculation was based on Lehr's formula for comparison between two groups, assuming equal treatment effects for the two experimental diets. The standard deviation (SD) of the change in liver fat was 1.95 and 2.42 in two of our previous trials (1,2). As the population in the NAFLD trial will differ (e.g. higher prevalence of type 2 diabetes) compared to these other trials, we assume a SD of 3 for the current calculation. Given that 5% liver fat is the cut-off for NAFLD, we considered a 2% difference between groups as clinically relevant. To detect a difference of 2%-points in liver fat between the control group and one experimental group, n=36 individuals per group are needed with  $\beta=0.80$  and  $\alpha=0.05$ . To allow for 25% drop-out, n=50 individuals per group will be included. Thus, a total of n=150 individuals will be randomized.

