### 6.1. Primary outcome

For the primary outcome a General Linear Model (GLM) will be applied using  $\Delta$ liver fat (%) between month 12 and baseline as the dependent variable, treatment group as factor and type-2 diabetes status (yes/no), gender (male/female) and baseline liver fat content (%) as included covariates. The GLM will be applied for the ITT-population (defined above) as well as for the PP-population (defined above). Independent samples post-hoc t-tests will follow if between-group statistical significance is observed.

A sensitivity analysis will be conducted for the primary outcome in both the ITT- and PP-population, with weight change included as an additional covariate in the GLM.

Treatment effects will be presented as mean or median differences (%) with 95% confidence intervals and with corresponding p-values.

When assumptions of the GLM are not satisfied, the Willett's residual method will be applied, followed by Mann-Whitney U post-hoc tests.

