## **6.2 Secondary and exploratory outcomes**

For secondary and exploratory outcomes GLMs will be applied using  $\Delta$ values between baseline and month 12 for each continuous variable (see point 4.2 and 4.3) as dependent variables and type-2 diabetes status (yes/no), gender (male/female) and baseline outcome values as included covariates in the model. Outcome values from 6 months follow-up will be presented descriptively.

The GLM will be applied for the ITT-population (defined above) as well as for the PP-population (defined above) for HbA1c, LDL cholesterol, triglycerides and systolic- and diastolic blood pressure. For the remaining secondary and exploratory outcomes, a PP-population will be used. Independent samples post-hoc t-tests will follow if between-group statistical significance is observed.

Treatment effects will be presented as mean or median differences (%) with 95% confidence intervals and with corresponding p-values.

When assumptions of the GLM are not satisfied, the Willett's residual method will be applied (3), followed by Mann-Whitney U post-hoc tests.

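### SAP 6.1 moves the primary analysis from the GLM to a rank route on an undefined trigger, and leaves open whether the effect is a mean or a median difference

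*SAP*

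**What the plan says.** Section 6 (Analyses) sets a general rule: "Continuous variables will be tested for normality using the Shapiro-Wilk W test", and skewed data, defined as W below 0.95, "will be logarithmically transformed or analyzed non-parametrically, where appropriate". For variances it says "Homogeneity of variances between groups will be examined visually", with no threshold and no consequence.

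Section 6.1 (Primary outcome) fits a GLM to the 12-month change in liver fat, with diet group as factor and diabetes status, gender and baseline liver fat as covariates. Two further steps follow:

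- "Independent samples post-hoc t-tests will follow if between-group statistical significance is observed".
- "When assumptions of the GLM are not satisfied, the Willett's residual method will be applied, followed by Mann-Whitney U post-hoc tests".

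On reporting: "Treatment effects will be presented as mean or median differences (%) with 95% confidence intervals".

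Section 6.2 repeats the same fallback for secondary and exploratory outcomes, and again "Treatment effects will be presented as mean or median differences". Section 2.1 sized the trial "To detect a difference of 2%-points in liver fat between the control group and one experimental group".

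**The concern.** Four things that determine the primary result are not fixed.

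1. **Trigger.** Section 6.1 does not say which GLM assumptions count, how they are checked, or what counts as failure. The W cut-off in section 6 is set for continuous variables. It is not stated to apply to model residuals, and 6.1 does not refer to it.
2. **Three-group test on the rank route.** The GLM compares three diets before any pairwise test. The fallback names only a pairwise test, so the analyst would have to supply the overall test.
3. **Effect measure.** A mean difference and a median difference are different quantities when the change is skewed. Only the mean difference corresponds to the sizing.
4. **Pairwise step on the main route.** Independent-samples t-tests carry no covariates, so they drop the baseline and stratification factors that the GLM adjusts for.

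At stake is whether a reader can be sure that the primary test and effect measure were chosen before the results were known.

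**Working it through.** **The plan's own figure.** Lehr's formula with SD 3 and difference 2 (section 2.1): n = 16 × 3² / 2² = 16 × 9 / 4 = 36 per group, as stated. The usual normal formula at two-sided 5% also gives 36, with power 0.807. Dropout: 36 / 0.75 = 48, so 50 is adequate; 50 × 0.75 = 37.5, hence 37 completers per group below. The sizing is sound, and it concerns a difference in means.

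**Can the section 6 options be applied to the 6.1 variable?** The dependent variable is a change. In the skewed settings below, 57% of changes are at or below zero with no diet effect and 75% with a 25% reduction, so a log cannot be taken of it directly. That leaves the rank route, with its trigger undefined.

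**Simulation inputs.** The SAP gives no distribution for liver fat, so these are assumptions:

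- Baseline is log-normal with median 7, 6 or 5% and SD of log 0.35, 0.6 or 0.8 (settings A, B, C).
- Month 12 = baseline × diet factor × mean-one log-normal noise (SD of log 0.35). The SD of change is then 2.6-3.3, close to the planned 3.
- Three arms of 37; both experimental diets equal, as section 2.1 assumes; diabetes status and gender without effect.
- The rank route is completed with a Kruskal-Wallis test on residuals of change on the covariates, because the SAP names none.

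Repeat runs differ by a point or two.

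**Type I error (nominal 5%)**

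| Rule | A | B | C |
|---|---|---|---|
| GLM always | 4.7% | 4.5% | 4.4% |
| Residual-rank always | 4.6% | 4.6% | 4.8% |
| Fixed rule: W < 0.95 on residuals, then rank | 5.2% | 4.9% | 5.1% |
| Either 6.1 route significant | 6.2% | 6.2% | 7.2% |

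With normal change the last row is 6.0%. A further run gave 5.7-7.4% for that row and 4.9-5.5% for a fixed W rule.

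**Does the choice matter when there is an effect?** With a true 25% reduction, the GLM and the rank route differ in significance in 5%, 10% and 15% of trials. W on the change and W on the GLM residuals fall on different sides of 0.95 in 23%, 18% and 6% (with no effect: 17%, 12%, 4%).

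**Size of the reported effect, same data (percentage points)**

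| Measure | A | B | C |
|---|---|---|---|
| Mean difference | -1.86 | -1.77 | -1.70 |
| Raw median difference | -1.56 | -1.24 | -0.99 |
| Hodges-Lehmann shift on residuals | -1.59 | -1.38 | -1.17 |

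The median difference is smaller than the mean by 1 - 1.56/1.86 = 16%, 1 - 1.24/1.77 = 30% and 1 - 0.99/1.70 = 42%.

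**Pairwise step.** Power for control against one diet is 0.89, 0.84, 0.75 with a contrast from the GLM (ordinary errors) and 0.88, 0.80, 0.68 with the separate t-test. With normal change correlated -0.3 to -0.5 with baseline it is 0.83-0.90 against 0.80-0.82. With zero correlation the contrast is about one point lower.

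**The case against.** The strongest reply is that 6.1 is the specific rule and section 6 the general one. Section 6 also governs descriptive presentation, and the rank route in 6.1 can be taken as its non-parametric option. On that reading there is an order: GLM first, residual-rank second. This is fair. A reader might infer that the two sections flatly contradict each other; the text does not force that. The reading does not, however, supply a criterion for the trigger, a three-group rank test or a single effect measure.

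Three other stronger readings do not hold:

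- **That the primary effect could become a ratio.** Section 6.1 promises only mean or median differences, and no log-level model is described. Adding one as a third route raises the free-choice type I error to about 7-10%, but that figure rests on a model outside the SAP.
- **That the plan inflates type I error.** Always picking the significant route is an upper bound, not the stated procedure, and a fixed W rule holds about 5%.
- **That everything turns on taking W pooled or by arm.** With normal change it would matter: W falls below 0.95 in 4 of 10,000 trials pooled over 111 subjects, but in at least one arm in 26%. Under the skewed settings pooled W on the change fires in 46-98% of trials, so the switch matters either way. The SAP mentions groups only for variances.

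It is also fair to say that dropping the fallback is partly preference. A fixed fallback would cure the fault and has more power under skew, so it is offered below as an alternative.

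**Conclusion.** The point holds in this limited form: the trigger in 6.1 is undefined and not tied to the W rule, the rank route lacks a three-group test, the effect measure is open, and the post-hoc t-tests abandon the model's adjustment. The error-rate consequence is modest, at most about 6-7% instead of 5% for a free choice between the two routes. The larger consequence is for interpretation. In the assumed settings the two routes disagree on significance in 5-15% of trials, and the median difference is 16-42% smaller than the mean difference on which the trial was sized. These figures rest on assumed distributions; they show the scale of the risk and do not predict this trial. The gap in the text rests on no assumption. It is a cheap improvement, not a threat to the design.

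**What to change.** Replace the analysis and fallback text in 6.1 with wording such as:

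> The primary analysis is the GLM on change in liver fat with diet group, type 2 diabetes status, gender and baseline liver fat, pooled over imputations by Rubin's rules, whatever the Shapiro-Wilk test shows. The effect is the adjusted mean difference in percentage points with 95% CI. If the three-group test is significant, pairwise comparisons are contrasts from this same model.

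For this outcome, remove the W switch, the median alternative and the separate t-tests. Keep the residual-rank analysis (Kruskal-Wallis, then Mann-Whitney U with the Hodges-Lehmann shift) as a prespecified sensitivity analysis that does not replace the primary. Running it in the per-protocol population avoids pooling ranks over imputations. Apply the same rule in 6.2, with each outcome's own adjusted mean difference. Robust (HC3) standard errors are optional.

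**Cost.** SAP wording only; no new data and no change in sample size. Under strong skew the GLM has less three-group power than the rank route: 0.92, 0.87, 0.78 against 0.92, 0.90, 0.86 in settings A, B, C, a loss of 0, 3 and 8 points.

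**Alternative.** If the sponsor prefers to keep a fallback, fix it before any data are seen: W below 0.95 on the GLM residuals pooled over arms, one named three-group rank test and one effect measure.

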## 1. Introduction

Randomized controlled studies investigating the impact of replacing dietary carbohydrates with polyunsaturated fat (PUFA) on liver fat content and cardiometabolic risk in individuals with prediabetes and T2D are lacking. Also, the effects of a Healthy Nordic Diet on liver fat content and glycemic control have not been investigated. This study therefore aims to:

- Investigate the effects of the diets on liver fat content (primary aim)
- Investigate the effects of the diets on pancreatic fat, visceral fat, lean tissue, glycemic and lipid control
- Investigate the effects of the diets on plasma markers of de novo lipogenesis (DNL) and desaturation (i.e. stearoyl-Coenzyme desaturase 1, SCD-1) as well as on hepatic DNL using MRI spectroscopy
- Investigate gene-diet interactions, especially if common gene variants (e.g. in PNPLA3) known to increase liver fat and dyslipidemia, may modify the dietary effects.
- Perform lipidomic analyses to identify potential mechanistic pathways that may associate with diet-induced changes in liver fat, pancreatic fat, visceral fat, insulin sensitivity, dyslipidemia or DNL

Our hypothesis is that a customized diet will effectively reduce liver fat through suppression of hepatic DNL and SCD-1 activity, and thereby improve atherogenic dyslipidemia, insulin resistance and hyperglycemia in individuals with prediabetes and T2D.

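### Each of 24 secondary change variables is tested at 5% with no ordering, no gate on the primary outcome and no nominal label, so a significant secondary result should be read as supportive only

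*SAP*

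**What the plan says.** SAP section 6 sets a single level for all analyses: an alpha "value of 0.05 is set as the significance level". It does not distinguish primary from secondary or exploratory outcomes.

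Section 6.2 gives the secondary and exploratory outcomes one common treatment: "For secondary and exploratory outcomes GLMs will be applied using" the change from baseline to month 12 of each continuous variable. "Independent samples post-hoc t-tests will follow if between-group statistical significance is observed". Effects are reported "with 95% confidence intervals and with corresponding p-values".

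The only conditional step is therefore inside a single outcome, from the overall three-group test to the pairwise tests. Nothing operates across outcomes. There is no order, key secondary outcome, division of alpha or dependence on the liver fat result, and no statement that secondary p-values are descriptive. The exploratory label is kept for the separate outcomes of section 4.3, which section 6.2 analyses in the same way.

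Section 6.2 does single out five secondary outcomes for analysis in both the ITT and the PP population: HbA1c, LDL cholesterol, triglycerides, and systolic and diastolic blood pressure. The remaining secondary outcomes are analysed in the PP population only.

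**The concern.** With two dozen variables each held to 5%, some will probably cross the threshold by chance even if the diets do nothing to them. The SAP separates secondary from exploratory outcomes by name, so a reader will give secondary results more weight. The plan, however, gives no rule that justifies the extra weight.

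This matters because the hypothesis in section 1 reaches beyond liver fat. It expects the customized diet to "thereby improve atherogenic dyslipidemia, insulin resistance and hyperglycemia in individuals with prediabetes and T2D". Several section 4.2 variables bear on each part of that statement, and the plan does not say which would decide it. If the liver fat comparison is not significant, the plan as written still lets an isolated secondary finding be called significant on the same terms as the primary. A reader would have no agreed basis for discounting it.

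**Working it through.** **The plan's own figure.** The SAP states no error rate across the secondary outcomes. Its only derived figure is the sample size in section 2.1, which supplies the group size used below. Lehr's formula with SD 3 and difference 2 gives 16 × 3² / 2² = 36 per group, as stated. Allowing for 25% drop-out, 36 / 0.75 = 48, against 50 planned. Expected completers are 50 × 0.75 = 37.5 per group.

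**Counting the variables (section 4.2).**
- Ten single variables: three MRI tissue volumes (the first is "Between-group changes in visceral adipose tissue mass between baseline and month 12"), body weight, HbA1c, HOMA-IR, fasting glucose, fasting insulin, systolic and diastolic blood pressure.
- Six lipids: "total cholesterol, LDL cholesterol, triglycerides, HDL cholesterol, apoB and apoA1".
- Five inflammatory markers: "CRP, Tumor Necrosis Factor Alpha-receptor 1 and 2, Interleukin-1 receptor antagonist, Fibroblast growth factor 21".
- Pancreatic fat, change in FMD and change in PWV: three.

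Total: 10 + 6 + 5 + 3 = 24.

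**Independent tests, no diet effect on any of them.**
- Chance of at least one significant overall test: 1 − 0.95^24 = 1 − 0.292 = 0.708, or 71%.
- Expected number significant: 24 × 0.05 = 1.2. This holds whatever the correlation.

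**Correlated outcomes.** The SAP gives no correlations, so they are assumed. The table comes from 6,000 simulated null trials of 3 × 37 participants, with 24 equally correlated normal outcomes and an overall F-test per outcome at 0.05. The lower rows add the plan's next step, pairwise t-tests only after a significant overall test. They count only outcomes where an experimental diet is significantly better than control, with every outcome oriented so that one direction means improvement.

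| At least one false result | 0 | 0.3 | 0.5 | 0.7 | 0.9 |
|---|---|---|---|---|---|
| Any significant overall test | 71% | 60% | 47% | 33% | 17% |
| Either experimental diet better than control | 41% | 29% | 22% | 15% | 7% |
| Customized diet better than control | 26% | – | 14% | – | 4% |

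A repeat simulation gave 72%, 48% and 17% for the first row at correlations 0, 0.5 and 0.9, and 39%, 22% and 8% for the second. The second row is therefore about 40% at 0 and about 8% at 0.9. The expected number of outcomes in that row is about 0.5.

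**Sensitivity of the first row.** A separate simulation used 4,000 null trials per setting, 38 per group and three covariates in the model. It gave 47% at a common correlation of 0.5. With outcomes grouped by domain (assumed correlation 0.5 to 0.9 within a domain, 0.1 to 0.3 between domains), the rate ran from 64% down to 44%.

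**The case against.** The strongest reply is that this is a trial with one primary outcome. The sample size rests on that outcome alone, and testing the secondaries afterwards does not inflate its 5%. The SAP never calls the secondary outcomes confirmatory, and it requires estimates and confidence intervals as well as p-values. Whether such a trial needs a formal hierarchy is a matter of judgement. All of this stands, and for that reason the remedy below is a label, with an ordered list only as an option.

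Three stronger readings are tempting, but the SAP does not support them.

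- A reader might infer that a trial of ineffective diets would report a secondary improvement about half the time. The 47% counts any significant non-directional overall test, including worsening and differences only between the two experimental diets. The rate for a false advantage over control is about 22% at the same correlation.
- A reader might count 26 tests by adding FMD and PWV values at month 12. Section 6.2 specifies models for change values only and states no test for those two, so 24 is the firm count.
- A reader might take section 1 to mean that any one lipid or glucose variable would establish the corresponding claim. Section 1 states a hypothesis and names liver fat as the primary aim. The SAP leaves the deciding variable open; it does not say that any one suffices.

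The reply does not remove the gap. One significance level covers everything in section 6, and the document does not say that a secondary result below 0.05 means less than a primary one.

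**Conclusion.** The point holds as a weakness in how secondary results may be read, and not as a defect in the primary analysis. At an assumed common correlation of 0.5, with no diet effect on any secondary variable, the plan produces at least one significant overall test in about 47% of trials and at least one false advantage over control in about 22%. The ranges are wide: 71% to 17% for the former and about 40% to 8% for the latter, as the correlation goes from 0 to 0.9. Even the lowest of these figures is above 5%. The count of 24 omits the second analysis population for five outcomes, the subgroup analyses, the section 4.3 outcomes and the correlations of section 6.3.

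**What to change.** Add to section 6.2: *Only the primary outcome is tested in a confirmatory way. All secondary and exploratory outcomes are reported as estimates with 95% confidence intervals and nominal p-values, labelled supportive or exploratory. No claim of an established diet effect rests on them.*

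If the sponsor wants confirmatory secondary claims, it may instead fix a short ordered list before unblinding. The list should be drawn from the outcomes already given an ITT analysis (HbA1c, LDL cholesterol, triglycerides, systolic and diastolic blood pressure). They would be tested in the ITT population, and only if the overall three-group ITT test of liver fat is significant. Two details matter. The gate has to be that overall test, because section 6.1 names no single primary contrast. Outcomes analysed only in the PP population, such as HOMA-IR, should stay off the list so that the sequence does not mix populations.

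The change is one paragraph of SAP text and needs no extra data, participants or analyses. The price is that secondary outcomes outside any such list cannot be claimed as established effects.
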